1.0 INTRODUCTION AND STUDY RATIONALE

1.1 Breast Cancer and Screening

Breast cancer is the second leading cause of cancer mortality in women, and the American Cancer Society estimates 232,670 new cases of invasive breast cancer in women in 2014 and 2360 new cases in men (1). Since 1990, the mortality rate from breast cancer has decreased more than 30% in the United States (2), and this is likely related to both the implementation of screening mammography and significant advances in the treatment of breast cancer (3). Mammography remains the standard of care for early detection of breast cancer prior to clinical symptoms, facilitating treatment of malignancy when it is more likely curable; however, this may also result in a certain amount of overtreatment (7-10). Additionally, certain women have been shown to benefit from additional screening with contrast enhanced breast (MRI) (11); therefore, a given patient's screening regimen is optimized after discussion with a health care professional regarding personal risk assessment as well as the benefit and potential harms of various imaging studies. Several randomized controlled trials and meta-analyses have shown a reduction in breast cancer mortality with general agreement of a 15 to 20% relative risk reduction in breast cancer mortality resulting from invitation to screen (12-17).

1.2 Limitations of Screening Mammography

While mammography has shown proven benefit it is not a perfect screening test, with documented limitations (18-28) including false negative rates ranging from 6 to 46% (4;29-31). Retrospective and prospective studies have shown screening breast MRI is valuable for early detection in women at increased risk for breast cancer (32-39). Breast MRI has been shown to have a higher sensitivity for detecting breast cancer (71-93.8%) when compared to mammography (19-58.8%) (33,36-40). One condition where screening might be more likely to fail is in women with dense breasts. According to the breast cancer surveillance consortium data from 1994-2009, false negative rates for mammograms categorized as heterogeneously dense or extremely dense breasts were 50.56% and 13.93% respectively as compared to exams categorized as scattered fibroglandular tissue 32.25% and almost entirely fat 3.25%.

1.3 Breast Density and Screening

Since 2009, nineteen states have enacted dense-breast legislation requiring mammography providers to notify women categorized as having dense breast tissue about their condition. There is also a bill proposed in the US House currently. There is little evidence to direct supplemental or alternative imaging evaluation in patients with dense breast tissue who are not eligible for high risk screening with contrast enhanced breast MRI. The Digital Mammography Imaging Screening Trial (DMIST) compared film mammography with digital mammography to reveal a similar accuracy between the two modalities for the general screening population (41). However, digital mammography was more accurate than film mammography in pre- or peri-menopausal women, women with dense breasts, and women under the age of 50 (42). Mean glandular dose per view averaged 2.37 mGy for film mammography and 1.86 mGy for digital mammography in DMIST (43). Breast density has been associated with decreased sensitivity of mammography 68% in dense breasts versus 85% in non-dense breasts (4).

According to the breast cancer surveillance consortium data from 1994 to 2009, approximately 38.65% of women have heterogeneously dense and 9.56% women have extremely dense breasts. Aside from the use of digital mammography little data is available to direct additional or alternative imaging evaluation in this population.

1.4 Contrast Enhanced Mammography

Contrast enhanced mammography was first described in 1985 by Watt et al. utilizing digital subtraction angiography of the breast (44,45). This technique is based on the principle of digital subtraction between two images. One of the images has morphological data and the second image has information relative to breast vascularization. Weidner et al demonstrated the hypervascularity of invasive malignant breast tumors in 1991 (46). Initial studies focused on temporal subtraction CE mammography (47-50); however, no significant difference has been shown between the kinetic enhancement patterns observed for malignant or benign breast lesions. Dual-energy CE mammography was first described in 2003 by Lewin et al as an alternative to the temporal subtraction technique (51). This technique is based on the interaction between gamma rays and iodine. A “high energy” image above the k edge of iodine (33.2 keV) is obtained to distinguish vascular structures after iodine contrast administration. A “low energy” image (below 33.2 keV) is obtained for morphological information. The digital subtraction of these images highlights the vascularized structures similar to a temporal subtraction method. This technique allows for bilateral breast imaging after a single contrast administration. Dromain et al showed that DE CE digital mammography had a higher sensitivity (93%) than mammography alone (78%) with no reduction in specificity (63%) (4). This group subsequently showed increased diagnostic performance in 6 readers with better detection of malignancy and no increase in false positives with the addition of DE CE digital mammography with or without ultrasound (3). Recently, Jochelson et al compared DE CE digital mammography with breast MRI in patients with known breast carcinoma to reveal similar levels of primary tumor detection (6). MRI detected additional ipsilateral lesions better than DE CE digital mammography (6). However, CE DE digital mammography had a higher specificity with fewer false positives (6). The positive predictive value of an enhancing lesion was higher with DE CE digital mammography than for MRI (97% vs 85%, $p<0.01$) (6). These preliminary results suggest that DE CE digital mammography may be a feasible adjunct or an alternative to routine breast screening with conventional digital mammography in certain groups such as the population with dense breasts.

2.0 OBJECTIVES

Primary:

- To determine the accuracy of DE CE mammography when compared to full field digital mammography (FFDM) in patients with increased breast density (BI-RADS category c or d breast density).

Secondary:

- To assess interobserver and intraobserver variability observed with DE CE digital mammography as compared to FFDM. We hypothesize that DE CE digital

mammography assessment will have less interobserver and intraobserver variability than FFDM.

- To evaluate any breast cancer identified by each modality including pathologic diagnosis, histologic grade, tumor size, receptor profile, axillary nodal status, and distant metastases.
- To determine through questionnaires and study screening assessments whether DE CE digital mammography has associated factors that make it a less desirable patient experience than FFDM, and determine the acceptability of a randomized screening trial to compare the two modalities.

3.0 STUDY DESIGN OVERVIEW

3.1 Study Design

The proposed prospective pilot study will invite women meeting eligibility criteria to undergo screening digital mammography and DE CE digital mammography. This trial is unique because to our knowledge this technology has not been assessed in women with BI-RADS category c and d dense breasts as an adjunct to routine screening. We will determine the potential of this imaging technique as an alternative or adjunct to screening mammography in this patient population. Patients will undergo bilateral digital mammography with 4 views and DE CE digital mammography.

[figure not shown]
We hypothesize that DE CE digital mammography will have improved diagnostic accuracy when compared to FFDM in patients with increased breast density. Sensitivity, specificity, positive predictive values (PPV1 and 3), negative predictive value (NPV), call back rate, false negative rate, and accuracy will be assessed.

This imaging technique is hypothesized to improve detection of masses (particularly those that enhance post contrast administration) in patients with dense breasts; thereby decreasing the false negative rate. Additionally, the ability of this technique to demonstrate contrast enhancement of masses may decrease call back rate as compared with FFDM. This trial is unique because to our knowledge this technology has not been assessed in this group of patients and this study will provide data to prepare for a larger clinical trial to determine the accuracy of this novel imaging technique as an alternative or adjunct to screening mammography in this patient population.

Figure 1 – Study Design

SCHEMA

Patient with heterogeneously or extremely dense breasts meeting eligibility criteria consented for study.

3.2 Endpoints

Primary:

- Sensitivity, specificity, positive predictive values (PPV1 and 3), negative predictive value (NPV), call back rate, false negative rate, and accuracy will be assessed.

Secondary:

- Each study will be interpreted by 4 radiologists with varying levels of experience blinded to results with separation of time. Interobserver variability will be assessed utilizing raw data agreement and Kappa coefficient.

3.3 Study Duration and Dates

Two years.

3.4 Safety and Efficacy Monitoring

This prospective pilot study will be approved by the UAB Institutional Review Board with a data safety monitoring plan approved by the UAB CCTS. In addition, approval by the UAB Radiation Safety Committee is necessary since patients who participate will be undergoing additional radiation associated with the DE CE digital mammographic study. The estimated dose from the combined low and high energy levels for DE CE is reported as 1.2 times that delivered during a routine single mammographic view (53). Imaging will be performed on GE Senographe DS and Essential mammography units with software upgrades for DE CE digital mammography. The UAB breast imaging section is an ACR accredited Breast Center of Excellence with mammography equipment certification by the FDA and ACR. The device under investigation is considered a non-significant risk device per the 21 CFR 812.3 definition 1) it is not intended as an implant; 2) is not purported or represented to be for a use in supporting or sustaining human life; 3) is not for a use of substantial importance in diagnosing, curing, mitigating, or treating disease, or otherwise preventing impairment of human health; 4) and it does not otherwise present a potential for serious risk to the health, safety, or welfare of a subject." Non-significant risk devices do not require a formal Investigation Device Exemption.

3.5 Ethical Considerations

This study will be conducted in accordance with Good Clinical Practice, the Declaration of Helsinki, and 21CFRPart50 – Protection of Human Patients, Part 56 – Institutional Review Boards, and the other applicable local ethical and legal requirements.

The Ethics Review Committee/Institutional Review Board (IRB) must be constituted according to Code of Federal Regulations (CFR).

The IRB must be informed by the principal Investigator of all subsequent protocol amendments and of serious or unexpected AEs occurring during the study which are likely to affect the safety of the patients or the conduct of the study. Approval for such

changes must be transmitted in writing to the Sponsor (UAB) via the Principal Investigator.

The Principal Investigator or designee will notify the IRBs and investigators when the study is placed on “hold”, completed, or closed to further patient enrollment.

3.6 Informed Consent

The principles of informed consent in the current edition of the Declaration of Helsinki will be implemented in this study. A written informed consent will be obtained in accordance with 21CFR50.25 and 21CFR50.27 before the protocol – specified procedures are carried out. Patients, their relatives, guardians or, if necessary, legal representatives must be given ample opportunity to inquire about details of the study.

The consent form generated by the Principal Investigator must be approved (along with the protocol) by the applicable IRB. Consent forms must be in a language fully comprehensible to the prospective patient. The consent form should be signed and dated by the patient or the patient’s legally authorized representative, and the investigator. Each patient’s signed informed consent form must be kept on file by the investigator for possible inspection by Regulatory Authorities and sponsor (UAB).

3.7 Confidentiality

Patient names will not be supplied in the data. Only the patient number and patient initials will be recorded in the CRF, and if the patient name appears on any other document (e.g., laboratory report), it must be obliterated. Study findings stored on a computer will be stored in accordance with local data protection laws. The patients will be informed that representative of the independent IRB, or regulatory authorities may inspect their medical records to verify the information collected, and that all personal information made available for inspection will be handled in strictest confidence and in accordance with local data protection laws.

The investigator will maintain a personal patient identification list (patient numbers with the corresponding patient names) to enable records to be identified.

4.0 SELECTION OF PATIENTS

4.1 Number of Patients

Approximately 200 patients should be enrolled in this study. It is planned to recruit this sample in one center.

4.2 Inclusion Criteria

Patients meeting all the following criteria will be considered for enrollment into the study:

1. Have heterogeneously or extremely dense breasts (BI-RADS category c or d).
2. Have GFR >60.
3. Are 19 years of age or greater.
4. Signed informed consent.

4.3 Exclusion Criteria

Patients presenting with any of the following will not be included in the study:

1. Have a history of iodinated contrast allergy.
2. Are pregnant or lactating as determined by routine standard practice.
3. Have a personal history of breast cancer;
4. Have a history of prior breast excisional biopsy. (Patients with a history of core needle biopsy will not be excluded).
5. Have a history of prior breast reduction mammoplasty surgery.
6. Have a history of prior breast augmentation surgery.
7. Mental condition rendering the subject unable to understand the nature, scope, and possible consequences of the study.

4.4 Patients of Reproductive Potential

The patient must not be pregnant or breast-feeding at enrollment in the study. The patient's will be asked if there is any possibility that they could be pregnant. Serum pregnancy tests will be obtained if there is a possibility of pregnancy as per routine breast imaging protocol.

5.0 STUDY TREATMENTS

5.1 Overall Plan

The proposed prospective pilot study will invite women meeting eligibility criteria to undergo screening digital mammography and DE CE digital mammography. This trial is unique because to our knowledge this technology has not been assessed in women with BI-RADS category c and d dense breasts as an adjunct to routine screening, and to determine potential of this imaging technique as an alternative to screening mammography in this patient population. Patients will undergo either bilateral digital mammography with 4 views or bilateral digital mammography with 4 views plus DE CE digital mammography. Dual-energy CE digital mammography will be performed with bilateral craniocaudal and mediolateral oblique views at high and low energy levels. These images will be obtained after iodinated contrast administration. Intravenous injection of iodinated contrast agent (Omnipaque 350 (iohexal, GE, Shanghai, China) at a dose of 1.5 mL per kilogram of body weight will be injected at a rate of 3mL/sec (similar dose used for computed tomography studies). Standard departmental protocols for contrast administration will be followed. Imaging will begin 2.5- 5.0 min after contrast administration. Case report forms (CRFs) will be completed for each imaging study to record technique, views, dose, breast compression force, compressed breast thickness and image time. Screening digital mammogram images will be initially read by a radiologist specialized in breast imaging with 5 to 25 years of breast imaging

experience. A different breast radiologist will read the DE CE digital mammogram with a routine screening interpretation of only the low energy views initially. Subsequently, the entire DE CE digital mammography exam will be interpreted with all images by the same reader. Readers will interpret their designated study independently blinded to the additional study and results will be documented on the CRFs. Additional clinical work up will be performed based on both studies after the initial independent reads. All lesions will be further evaluated by standard of care. Both digital mammograms and DE CE mammograms will be assessed for quality. Truth will be determined using pathologic diagnoses when available or one year negative follow-up imaging. Calculations will be performed for sensitivity, specificity, negative predictive value, positive predictive value 1 for call back (PPV1), positive predictive value 3 for biopsy performed (PPV3), cancer detection rate, false negative rate, and call back rate.

To evaluate for interobserver and intraobserver variability, all studies will be read by 2 additional radiologists blinded to truth and randomized over time to minimize memory recall. Interobserver and intraobserver variability will be assessed utilizing raw data agreement and Kappa coefficient.

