7.0 EFFICACY AND SAFETY [

7.1 Efficacy Measurements

FFDM and DE CE digital mammography efficacies will be assessed by pathologic diagnosis when appropriate or by one-year follow-up mammography.

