8.0 STATISTICAL METHODS

- The primary endpoint of this study is to determine the accuracy of DE CE mammography when compared to full field digital mammography (FFDM) in patients with increased breast density (BI-RADS category c or d breast density).
- The statistical analysis will focus on calculations will be performed for sensitivity, specificity, negative predictive value, positive predictive value 1 for call back (PPV1), positive predictive value 3 for biopsy performed (PPV3), cancer detection rate, false negative rate, and call back rate.

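### Does a biopsy decision based on both studies, with no rule for crediting each biopsy, leave PPV3 undefined for FFDM and DE CE?

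*Combined protocol and SAP*

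**What the plan says.** Section 3.2 lists among the primary endpoints "positive predictive values (PPV1 and 3), negative predictive value (NPV), call back rate, false negative rate, and accuracy will be assessed". Section 8.0 states "The primary endpoint of this study is to determine the accuracy of DE CE mammography when compared to full field digital mammography (FFDM") and names "positive predictive value 3 for biopsy performed (PPV3") in its list of calculations, without giving the unit or the denominator for each modality.

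Section 5.1 sets the order of events. A different radiologist reads each study: "Readers will interpret their designated study independently blinded to the additional study and results will be documented on the CRFs". The DE CE reader looks first at the low-energy views alone, and then: "Subsequently, the entire DE CE digital mammography exam will be interpreted with all images by the same reader". After that, "Additional clinical work up will be performed based on both studies after the initial independent reads", and "All lesions will be further evaluated by standard of care".

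Section 7.1 adds: "FFDM and DE CE digital mammography efficacies will be assessed by pathologic diagnosis when appropriate or by one-year follow-up mammography".

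No section says how a biopsy enters the FFDM or the DE CE denominator when one read, both reads or neither flagged the lesion. Section 2.0 has a secondary objective on the cancers that each modality finds, but it gives no rule for biopsies.

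**The concern.** Two things look wrong.

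- **Attribution.** A comparison of modalities needs a PPV3 for each. If the crediting rule is open, the same biopsies can give different answers, and the rule could be chosen after the results are known.
- **Conditioning.** Being evaluated is not the same as being biopsied. A lesion flagged on FFDM alone might be spared biopsy because DE CE was reassuring, or the reverse. PPV3 would then describe the joint pathway and not either test alone.

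Section 3.1 says the pilot is to supply data for a larger trial, so a misread PPV3 could be carried into that design.

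**Working it through.** The documents give no biopsy rate, expected PPV3, power or test for PPV3, so there is no figure to reproduce. All counts below are assumptions chosen to show how the measure behaves. The formula is PPV3 = cancers / biopsies performed.

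**Assumed counts.** 12 biopsies with 3 cancers:
- flagged by both reads: 4 biopsies, 2 cancers
- FFDM only: 4 biopsies, 0 cancers
- DE CE only: 4 biopsies, 1 cancer

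**Step 1: three possible rules.**

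| Rule | FFDM | DE CE | Gap (points) |
|---|---|---|---|
| Any trigger: each biopsy counts for every modality that flagged it | (2+0)/(4+4) = 2/8 = 25.0% | (2+1)/(4+4) = 3/8 = 37.5% | 12.5 |
| Sole trigger: only biopsies flagged by that modality alone | 0/4 = 0% | 1/4 = 25.0% | 25.0 |
| No assignment: all biopsies count for both | 3/12 = 25.0% | 3/12 = 25.0% | 0 |

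**Step 2: vary the number of shared biopsies, b.** Hold the totals per modality (8 biopsies each, with 2 and 3 cancers) and the 2 shared cancers.
- Any trigger: 2/8 v 3/8 at every b, gap 12.5 points.
- Sole trigger: 0/(8−b) v 1/(8−b). The gap is 16.7 points at b = 2, 25.0 at b = 4 and 50.0 at b = 6.
- No assignment: 3/(16−b) for both, that is 21.4%, 25.0% and 30.0%. The gap is always 0.

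The spread from 0 to 50.0 points therefore comes from the second and third rules. Neither gives a modality's positive predictive value. No assignment counts lesions that the modality read as negative. Sole trigger discards every lesion that it flagged together with the other study. Only any trigger takes the proportion among the modality's own positives.

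**Step 3: can any trigger be applied?** Section 5.1 has both reads made blind and recorded before the joint work-up, so each biopsy can be traced back to the read or reads that flagged it. For DE CE the natural read is the full examination, not the low-energy views alone. Lesion-level tracing needs the lesion site. The CRF is not among the documents, so whether it records the site cannot be checked.

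**Step 4: influence of the joint work-up.** Let it change the number of benign biopsies by the same d in each modality. PPV3 is then 2/(8+d) v 3/(8+d).

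| d | FFDM | DE CE | Gap (points) | Ratio |
|---|---|---|---|---|
| −4 | 50.0% | 75.0% | 25.0 | 1.5 |
| −2 | 33.3% | 50.0% | 16.7 | 1.5 |
| 0 | 25.0% | 37.5% | 12.5 | 1.5 |
| +2 | 20.0% | 30.0% | 10.0 | 1.5 |
| +4 | 16.7% | 25.0% | 8.3 | 1.5 |

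The gap moves, but the ratio and the ranking do not. A reversal needs unequal effects. For example, averting 3 of the 4 FFDM-only benign biopsies and no others gives 2/5 = 40.0% v 3/8 = 37.5%. Nothing in the documents indicates whether that would happen, or in which direction.

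**Step 5: precision.** At assumed biopsy rates of 2% to 15%, 200 women give 200 × 0.02 = 4 to 200 × 0.15 = 30 biopsies. The exact 95% interval for 2/8 is 3.2% to 65.1%, and for 3/8 it is 8.5% to 75.5%. Sampling error is far wider than the 12.5-point gap.

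**The case for a change.** The strongest case for a change is that tracing biopsies back settles the denominator but not the conditioning. A lesion flagged by one study can still be biopsied, or spared, because of the other. The CRF items that section 5.1 spells out are technical, with only a general reference to results, and no lesion site or biopsy recommendation per read is named. A few extra fields would be cheap, and the original readers' recommendations cannot be collected once the reads have been combined.

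The conditioning stands: no attribution rule removes it. Three things limit what follows.

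- A biopsy recommendation at the screening read comes before diagnostic work-up. It is a proxy for the decision that PPV3 counts, so recording it would not repair PPV3.
- Section 3.1 considers DE CE as an addition to screening mammography as well as a replacement. For the added role, biopsy after both studies are seen is the relevant pathway. Only the replacement role needs the caution, and a label on the result supplies it.
- The loss is not total. The blinded read results are kept, and section 5.1 has all studies read by two further radiologists blinded to truth.

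**Conclusion.** No change to the plan is needed. The text is silent on attribution, but the ordinary definition of a predictive value fills the gap: a biopsy counts for each modality whose blinded read flagged the lesion. On the assumed counts that gives 25.0% v 37.5%, a gap that does not depend on how many biopsies are shared when the modality totals are fixed. Larger and zero gaps arise only under rules that an analyst would have no reason to choose.

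A PPV3 reported this way is conditional on the joint work-up, with unknown size and direction of effect. A competent report would say so and would show biopsies by which read flagged them. Call-back rate, woman-level PPV1, sensitivity and specificity can be assigned from the blinded reads and do not share the attribution problem. The specific hypotheses in section 3.1 concern the false negative rate and call-back, and the plan attaches no test or threshold to PPV3.

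The conclusion rests on two assumptions: that lesion site is recorded at each read, and that the women concerned had both examinations. On the second, section 3.1 gives every patient both, while section 5.1 allows FFDM alone. Those sections must be reconciled as a separate matter. Biopsies in women who had FFDM alone could not be influenced by DE CE.

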11.0 DOCUMENTATION AND USE OF STUDY FINDINGS

11.1 Documentation of Study Findings

A case report form will be provided for each subject.

All protocol-required information collected during the study must be entered by the investigator, or designated representative, in the case report form. Details of case report form completion and correction will be explained to the investigator. If the investigator authorizes other persons to make entries in the case report form the names, positions, signatures and initials of these persons must be supplied to the sponsor.

The investigator or designated representative should complete the case report form pages as soon as possible after information is collected, preferably on the same day that a study subject is seen for an examination, treatment, or any other study procedure. Any outstanding entries must be completed immediately after the final examination. An explanation should be given for all missing data.

A source data location list will be prepared prior to study start. This list will be filed in both the trial master file and the investigator study file and updated as necessary.

investigator.

The sponsor will retain the originals of all case report forms. The investigator will retain a copy of all completed case report form pages.

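### Does the absence of a written rule for women without one-year follow-up call for a change to the accuracy analysis?

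*Combined protocol and SAP*

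**What the plan says.** Section 5.1 ties further investigation to the index reads: "Additional clinical work up will be performed based on both studies after the initial independent reads". It then defines the reference standard: "Truth will be determined using pathologic diagnoses when available or one year negative follow-up imaging". Section 7.1 repeats the rule in other words, saying that "efficacies will be assessed by pathologic diagnosis when appropriate or by one-year follow-up mammography".

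Section 3.3 gives a total of two years and does not divide it into accrual and follow-up. On size, section 4.1 says "Approximately 200 patients should be enrolled in this study", at one center. The primary endpoints in 3.2 are a list: "Sensitivity, specificity, positive predictive values (PPV1 and 3), negative predictive value (NPV), call back rate, false negative rate, and accuracy will be assessed". Section 8.0 also lists measures ("The statistical analysis will focus on calculations will be performed for sensitivity, specificity, negative predictive value" and others). It sets no hypothesis test, threshold or missing-data rule. The only statement on missing data is a case report form instruction in 11.1: "An explanation should be given for all missing data". Section 3.1 gives the pilot's purpose: "this study will provide data to prepare for a larger clinical trial to determine the accuracy of this novel imaging technique".

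**The concern.** Labels arrive at different speeds. A recalled woman who is biopsied has pathology within weeks. A woman negative on both exams, or recalled but not biopsied, has no label until imaging at one year. If the database closes before some women reach one year, or some do not return, a labelled-only analysis keeps biopsied false positives and loses true negatives. Specificity then looks too low. Sensitivity tends to look too high, because cancers missed by both exams and never followed up are not counted.

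Specificity and accuracy are primary endpoints, and the estimates are meant to inform a larger trial, so a systematic error could be carried forward. A two-year total with no stated split leaves open whether every woman can reach one year. The two versions of the truth rule add to the doubt: 5.1 says imaging and 7.1 says mammography, which is the comparator's own modality.

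**Working it through.** **No figure to reproduce.** The documents give no power, prevalence, recall rate, biopsy rate or return rate. From the documents: 200 women, 24 months in total, one-year follow-up. Assumed: specificity 90% for both exams, 10-50% of false positives biopsied, uniform accrual, and both exams in every woman (3.1 says so, although one sentence in 5.1 reads as either/or).

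**Step 1: readings of the two years.**
- Accrual of 12 months plus 12 of follow-up: all 200 women reach one year (200/12 = 16.7 enrolled per month). Timing bias is 0.
- Two years of accrual with follow-up afterwards: all 200 again reach one year. Timing bias is 0.
- Two years in total with accrual over T > 12 months: the share reaching one year is f = 12/T, which is 0.80, 0.667 and 0.50 for T = 15, 18 and 24, or 160, 133 and 100 women.

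Only the third reading creates a timing problem.

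**Step 2: size under the third reading, labelled women only.** Let b be the share of false positives biopsied and v = b + (1-b)f the share of false positives that get a label.
- False positives of the two exams fully overlapping: specificity = 0.9f/(0.9f + 0.1v).
- Independent: neg = 0.9(0.9f + 0.1v), pos = 0.1v, specificity = neg/(neg + pos).

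Example, f = 0.5 and b = 0.5: v = 0.75. Overlapping: 0.45/0.525 = 85.7%, 4.3 points low. Independent: 0.4725/0.5475 = 86.3%, 3.7 points low.

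| Accrual (months) | Points low, independent | Points low, overlapping | Labelled women (independent) | Standard error, points |
|---|---|---|---|---|
| 12 | 0 | 0 | 200 | 2.1 |
| 15 | 0.2-1.0 | 0.2-1.1 | 161-164 | 2.3-2.4 |
| 18 | 0.4-1.9 | 0.4-2.2 | 135-140 | 2.5-2.6 |
| 24 | 0.8-3.7 | 0.9-4.3 | 102-110 | 2.9-3.0 |

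The standard error is sqrt(0.09/n), with n the number of labelled women. The shift passes one standard error only at 24 months and a high biopsy share. Overlapping, b = 0.3 gives 0.45/0.515 = 87.4% (2.6 low), and b = 0.4 gives 0.45/0.52 = 86.5% (3.5 low).

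**Step 3: non-return alone**, overlapping false positives, f = 0.95, 0.90, 0.80.
- If unbiopsied recalled women are lost at the same rate as read-negative women (b = 0.5): up to 0.2, 0.5 and 1.1 points low.
- If only read-negative women are lost (v = 1): 0.9f/(0.9f + 0.1) = 89.5%, 89.0% and 87.8%, so 0.5, 1.0 and 2.2 points low.

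**Step 4: the comparison of modalities.** Work-up is triggered by either exam and serves both. With equal biopsy rates among false positives the false difference is 0. An assumed 20% for FFDM against 50% for DE CE gives 0.7, 1.3 and 2.5 points at 15, 18 and 24 months (independent). The paired standard error at 200 women is sqrt(0.18/200) = 3.0 points. Nothing in the documents supports those unequal rates; 5.1 sends all lesions to standard-of-care evaluation.

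**Step 5: sensitivity.** At an assumed prevalence of 0.3-2%, 200 women yield 0.6-4 cancers. Two found of two has an exact 95% interval of 15.8-100%. One hidden cancer makes it two of three (67%, 9.4-99.2%). No missing-data rule makes that estimate precise.

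**Step 6: 5.1 against 7.1.** Mammography is a form of imaging, and 1.1 describes it as the standard of care for early detection, so one-year follow-up under usual care would ordinarily be a mammogram. The two rules can both be followed.

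**The case for a change.** The best case for acting is that the text is silent exactly where a diagnostic accuracy study needs a rule. Without one, the analyst decides after seeing the data whether to drop unlabelled women or count them as negative. The shift is systematic, so it does not average out when estimates are pooled or used for planning. The range above is also not the extreme: if every false positive had pathology and half the read-negative women were lost, specificity would fall to 0.45/0.55 = 81.8%. Section 6.0 schedules no one-year visit, and stating the split and a rule would cost only a few sentences.

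The silence is real, and writing the rule down would be good practice. The extreme case, however, needs accrual to fill the whole two years, which would leave half the women unable to meet the plan's own truth definition. It also needs every false positive biopsied and the unlabelled women discarded. The plan states none of these.

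The stronger remedies have a price. Restricting the analysis to women with one year plus an assumed 3-month window, with the end date fixed, leaves 200 x 9/12 = 150 women at 12-month accrual, where there is no timing bias to remove. At 24-month accrual it leaves 200 x 9/24 = 75, with a standard error of 3.5 points.

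**Conclusion.** The concern describes the text correctly but does not show a fault that needs correcting. A reference standard is named for every woman, including those negative on both exams, and the stated duration is compatible with all of them reaching it. Bias requires accrual beyond 12 months of a fixed two-year study, or non-return, together with a decision to drop unlabelled women.

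Under the assumed inputs the loss in specificity is 0 at 12-month accrual with full return, at most 2.2 points at 18 months, and at most 4.3 at 24 months, against standard errors of 2.1 to 3.0. Non-return of 5-20% costs up to 2.2 points. No bias in the comparison of modalities follows from the documents, and sensitivity is too imprecise at this size for the gap to matter.

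Call-back rate needs no truth label, and PPV3 uses women who have pathology. Section 8.0 sets no test or threshold that a shift of a few points could tip. In a single-center pilot of about 200 women, an analyst can tabulate labelled and unlabelled women by read result, using the explanations that 11.1 requires, and interpret specificity accordingly. The 5.1 and 7.1 wording is a clerical difference. The conclusion would weaken if accrual in fact ran close to 24 months with no later follow-up.
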